#### 9.4.2 Overall Sample Size

For the overall study design, we assume that the standard dose LPV/r regimen with or without RAL coupled with RBT-based anti-TB therapy will be superior to a double-dose LPV/r regimen with RIF-based anti-TB therapy. We estimate the virologic suppression rate at 48 weeks for the double-dose LPV/r treatment arm will be approximately 50%, for the LPV/r with RBT-based anti-TB therapy to be approximately 70%, and for the LPV/r plus RBT plus RAL arm to approach 80-90%. These numbers are based on the following considerations: 1) the standard of care in the US is to switch ART for a failing regimen at earlier time points based on viral load monitoring such that background rates of concomitant NRTI resistance are relatively low, while this is not the case in resource-constrained settings where viral load monitoring is less frequent or not routinely done; 2) there are only a limited number of drugs available for use in second-line therapy in most resource-constrained settings making it difficult to construct a second-line ART regimen with three or more known active drugs; 3) there may be more variability in PK with LPV/r coupled with RBT than has been previously appreciated, and this might compromise virologic outcomes; 4) there are insufficient data available to address this point, which is, in part, why we propose to do this study; and 5) we anticipate that there will be an appreciable rate of adverse effects of anti-TB treatment as well as of ARTs (especially in the double-dose LPV/r arm which could lead to poorer adherence and early treatment discontinuation, thus, lower efficacy) that might result in repeated episodes of short-term treatment interruption for management of side effects, as has been observed in A5221 and other TB treatment studies. For these reasons, the 85-90% virologic suppression rates reported at 48 weeks for studies in resource-rich settings may not be achievable in the context of active TB in resource-constrained settings.

Because the primary objective entails comparing virologic efficacy of Arm A versus Arm B and Arm C versus Arm A, we will have two hypothesis tests and will use an alpha-level of 0.025 for each test (thus, overall alpha-level = 0.05). If we assume the overall virologic efficacy of the double-dose LPV/r arm is 50%, and the standard LPV/r dosed arm coupled with RBT is 70% by 48 weeks (and 80-90% for LPV/r and RAL with RBT-based anti-TB treatment), 147 participants per arm will provide 90% power to detect a 20% difference in virologic response rates by 48 weeks between the double-dose LPV/r arm and the standard LPV/r plus RBT arm and adequate power for the comparison of the standard LPV/r plus RBT arm and adequate power for the comparison of the standard LPV/r plus RBT plus RAL arm compared to both other treatment arms. This assumes using a two-sample, two-sided 0.025-level asymptotically-normal binomial test.

Participants lost to follow-up will be considered as failures. Participants determined to have RIF-resistant TB isolates after enrollment will be taken off study, referred to their local clinician or clinical facility to receive best available local standard of care, and will not be replaced. Assuming that 3% of participants will have RIF resistance at entry and be taken off study, we will need to adjust the sample size to require 152 participants per arm. Adjusting the sample size again by 3% for interim analyses requires 157 participants per arm. Based on these data and assumptions, the estimated overall sample size will be 471 participants.

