### 1.2 Primary Objective

To compare rates of virologic suppression to < 400 copies/mL at 48 weeks for the two standard dose LPV/r and RBT arms versus the double-dose LPV/r and RIF arm.

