### 1.3 Secondary Objectives

- 1.3.1 To evaluate TB treatment outcomes (as measured by week 8 mycobacterial culture conversion, treatment failure at or after week 24, TB relapse/recurrence by week 72) between RBT-containing arms and the RIF-containing arm, to include the association between RBT or RIF exposure as well as other factors potentially associated with outcomes of TB treatment.

NOTE: TB treatment outcome measurements for participants who enroll with probable TB for whom week 8 mycobacterial culture conversion rates cannot be assessed will include either week 8 AFB smear conversion rate coupled with resolution of signs, symptoms, and radiographic abnormalities on which the diagnosis of probable TB was based or solely resolution of signs, symptoms, and radiographic abnormalities for participants with negative AFB smears or AFB smears that are not available at baseline; in addition, TB treatment failure at or after week 24, and TB relapse/recurrence by week 72 will be captured as TB outcome measures.

- 1.3.2 To compare rates of virologic suppression to < 50 copies/mL at 48 weeks for the two standard dose LPV/r and RBT arms versus the double-dose LPV/r and RIF arm.
- 1.3.3 To compare rates of virologic suppression to < 50 copies/mL and < 400 copies/mL at 48 weeks for standard dose LPV/r and RBT versus standard dose LPV/r, RBT, and RAL.
- 1.3.4 To compare safety and tolerability during TB treatment of double-dose LPV/r and RIF between the three treatment arms.
- 1.3.5 To compare the proportion of participants with virologic failure and time to virologic failure between the three treatment arms.

- 1.3.6 To compare the emergence of HIV-1 drug resistance mutations in gag, protease, reverse transcriptase (RT), and integrase in participants with virologic failure between the three treatment arms.
- 1.3.7 To compare the proportion of participants with TB drug-resistance among cases of TB treatment failure and relapse/recurrence of TB between the three treatment arms.
- 1.3.8 To characterize TB immune reconstitution inflammatory syndrome (IRIS) events.
- 1.3.9 To compare changes in CD4+ T-cell count, and proportion of participants who experience new AIDS-defining illness, HIV disease progression (defined as new AIDS-defining illness or death), or death between the three treatment arms.

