#### 9.5.2 Overall Study Monitoring

Early deaths, defined as those occurring within the first two months on study, will be monitored by the core team. The cumulative number of deaths during the first two months on study will be combined across the treatment arms and will be calculated on a monthly basis using a Kaplan-Meier estimator and reported to the core team. Should more than 15% of the number of participants enrolled die during the first two months on study, the team will request that the NIAID DSMB review the study for safety. This review will include both safety data and efficacy data through week 48, as available.

After the final SMC review of the PK and safety data during the dose-finding period in accrual period 1 participants, this study will be reviewed at least annually by the NIAID Data Safety and Monitoring Board (DSMB). This DSMB will receive a copy of the full accrual period 1 PK and safety interim analysis. For all annual reviews, the DSMB will be provided detailed information on safety (including mortality and regimen tolerability) and administrative aspects (accrual, baseline characteristics of participants, compliance with specimen storage, and retention). The first safety review will take place approximately one year after the final SMC review. The first efficacy review will be timed to occur while enrollment is ongoing so any required changes to the protocol may be made before accrual ceases. Thus, the first efficacy review will take place when approximately 25% of all participants have completed 48 weeks of follow-up. The timing of the first efficacy review will be decided at the first safety review. Efficacy reviews will employ group sequential monitoring of survival probabilities with boundaries defined by the Haybittle-Peto rule, with repeated 99.995% confidence intervals on the difference in proportions with HIV RNA level < 400 copies/mL at 48 weeks (Arm B versus Arm A and Arm B versus Arm C). For monitoring efficacy, there are three scenarios with respect to the confidence intervals:

1. The lower bound of the CI is >0%
2. The CI includes 0%
3. The upper bound of the CI is <0%.

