If the lower bound of the CI is >0%, then the experimental arm (A or C) is superior to Arm B with respect to the TB cure rate and the team intends to evaluate this finding in the context of the HIV RNA and toxicity endpoints to determine whether the study should be stopped. If the lower bound of the CI is >-10% but <0%, then Arm A or C is non-inferior to Arm B and the team intends for the study to continue to full accrual and follow-up as designed. If the lower bound of the CI is <-10%, then non-inferiority has not been demonstrated (yet) and the team intends to evaluate this finding in conjunction with predicted interval plots to evaluate the likelihood of demonstrating non-inferiority with trial continuation (e.g., evaluate futility). The team discussed the possibility of a futility analysis and decided the study should continue to full accrual and follow-up as designed since collecting secondary endpoints is desirable in this population.

The number and timing of reviews will depend on the accrual rate and will be decided in conjunction with the DSMB.

Reports on adverse events pooled over arms, but summarized by accrual period, will be provided to the Division of AIDS Medical Officer every 6 months.

When approximately 25% of participants have completed 48 weeks of follow-up, overall sample size will be re-evaluated based on the current study rate of HIV virologic suppression in Arm B only. If the suppression rate is much higher than the hypothesized 50%, the protocol team will need to consider increasing the sample size in order to have sufficient power to detect smaller treatment differences (since the hypothesized 70% HIV virologic suppression in Arm A will

still hold). If the suppression rate is much lower than the hypothesized 50%, the protocol team discussed the possibility of doing a futility analysis but decided that collecting secondary endpoints is desirable in this population given that Arm B is standard of care in many resource-constrained settings. As the primary endpoint involves comparisons with Arm B, monitoring the Arm B (standard of care/control) rate alone will not affect the alpha level for the primary objective.

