#### 9.6.2 Analysis of the Primary Objective

All participants enrolled into A5290 will be included in the analysis of all the overall study objectives regardless of any required dose adjustments for accrual period 1 participants. The protocol team discussed the effect of including participants enrolled during accrual period 1 who underwent dose adjustments in the final analysis of the primary endpoint. The protocol team acknowledges that it is possible that those enrolled during accrual period 1 who had low LPV concentrations and required a dose adjustment might have worse HIV viral load responses at week 48, or alternatively, those who underwent a dose adjustment of one or more study-provided drugs might have greater toxicity that could adversely affect adherence, early treatment discontinuation, and HIV viral load responses at week 48. There remains significant uncertainty around what the major drivers will be of the week 48 virologic outcomes in this setting, such that including all participants in an intent-to-treat analysis accounting for all factors that might have contributed to the endpoint, including low levels requiring dose adjustment, higher toxicity leading to non-adherence or dose interruptions, prolonged intensive TB treatment phase, etc. will be a part of the study analysis plan. The protocol team also acknowledges that it is possible that those enrolled during the accrual period 1 could be different than those enrolled during the accrual period 2. Besides seeking as homogeneous a population as possible, baseline tables of factors that could affect drug concentrations (e.g., sex, prior ART experience, body weight, etc.) will be summarized by accrual period.

The primary outcome variable will be the rates of virologic suppression at 48 weeks within each treatment arm. Participants lost-to-follow-up or without virologic data will be considered failures (i.e., not suppressed). The rate in the double-dose LPV/r arm will be separately compared to the standard dose LPV/r arms in two analyses. The rates between the two arms will be compared using an asymptotic normal binomial test (Arm A versus Arm B; Arm C versus Arm B).

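### Protocol 9.4.2 assigns the second 0.025 primary test to Arm C versus Arm A instead of Arm C versus Arm B, and its claim of adequate power for C versus A fails at the lower end of the assumed 80-90% range

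*Protocol*

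**What the plan says.** Protocol 9.4.2 is the only place where the 0.05 alpha is divided between contrasts. It opens that step with "Because the primary objective entails comparing virologic efficacy of Arm A versus Arm B and Arm C versus Arm A", then provides two hypothesis tests at 0.025 each.

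It assumes 48-week suppression of 50% in Arm B and 70% in Arm A, and expects the rate "for the LPV/r plus RBT plus RAL arm to approach 80-90" percent. It states that 147 per arm give 90% power for A versus B with a two-sided 0.025-level asymptotic normal test. It also claims, without a figure, "adequate power for the comparison of the standard LPV/r plus RBT plus RAL arm compared to both other treatment arms".

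Other sections define the primary comparison differently:

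| Section | Wording | Contrasts |
|---|---|---|
| 1.2 Primary Objective | "for the two standard dose LPV/r and RBT arms versus the double-dose LPV/r and RIF arm" | A vs B, C vs B |
| 9.5.2, interim efficacy | "Arm B versus Arm A and Arm B versus Arm C" | A vs B, C vs B |
| 9.5.2, sample-size re-evaluation | "As the primary endpoint involves comparisons with Arm B" | Arm B as comparator |
| 9.6.2, primary analysis | "using an asymptotic normal binomial test (Arm A versus Arm B; Arm C versus Arm B" | A vs B, C vs B |
| 1.3.3, secondary objective | "at 48 weeks for standard dose LPV/r and RBT versus standard dose LPV/r, RBT, and RAL" | C vs A |

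The primary hypothesis in SAP section 1.3 also sets the rifabutin arms against the rifampin arm. The clarification memo of April 2013 leaves 9.4.2 untouched.

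**The concern.** Sections 9.4.2 and 9.6.2 both plan two primary tests but disagree on the second. Taken literally, 9.4.2 gives 0.025 to a contrast that the objectives list as secondary, and nothing to C versus B, which 9.6.2 tests as primary. Together the two sections name three contrasts, with alpha stated for two. Running all three at 0.025 would give a nominal total of 3 × 0.025 = 0.075. The protocol should settle which contrasts carry the confirmatory alpha.

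The power claim is a separate problem. C versus B spans a gap of 30 to 40 percentage points, but C versus A spans only 10 to 20. A sample sized for a 20-point gap cannot be assumed to serve a 10-point one, so a reader relying on the claim may be over-assured about what the trial can say on adding raltegravir.

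**Working it through.** **Inputs (9.4.2):** Arm B 50%, Arm A 70%, Arm C 80-90%; 147 per arm; two-sided 0.025 (z = 2.2414); 90% power (z = 1.2816).

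**Formulas** (pooled variance under the null, no continuity correction), with p̄ the mean of the two rates and d their difference:

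- n per arm = [z_α·√(2p̄(1−p̄)) + z_β·√(p₁(1−p₁)+p₂(1−p₂))]² / d²
- power = Φ{ [d − z_α·√(2p̄(1−p̄)/n)] / √([p₁(1−p₁)+p₂(1−p₂)]/n) }

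**Step 1. Reproduce the plan's figure (A vs B, 50% vs 70%).**
n = [2.2414·√0.48 + 1.2816·√0.46]² / 0.04 = 146.7, so 147. Power at 147 is 90.1%. The inflation steps also reproduce: 147/0.97 → 152, 152/0.97 → 157, and 3 × 157 = 471. The formula therefore matches the plan's calculation.

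**Step 2. C vs B at 0.025, 147 per arm.**
At 50% vs 80%: (0.30 − 2.2414 × 0.05564)/0.05281 = 3.32, power 99.96%. It is higher still at 85% and 90%.

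**Step 3. C vs A at 0.025, 147 per arm (Arm A 70%).**
- Arm C 80%: (0.10 − 2.2414 × 0.05051)/0.05017 = −0.263, power 39.6%
- Arm C 85%: (0.15 − 2.2414 × 0.04871)/0.04792 = 0.852, power 80.3%
- Arm C 90%: (0.20 − 2.2414 × 0.04666)/0.04518 = 2.112, power 98.3%

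**Step 4. Alternative alpha and sample size for C vs A.**

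| n per arm | Two-sided alpha | Arm C 80% | Arm C 85% | Arm C 90% | Arm C rate for 80% power |
|---|---|---|---|---|---|
| 147 | 0.025 | 39.6% | 80.3% | 98.3% | 85.0% |
| 147 | 0.05 | 50.8% | 87.3% | 99.2% | 83.7% |
| 157 | 0.025 | 42.2% | 83.1% | 98.8% | 84.5% |
| 157 | 0.05 | 53.5% | 89.3% | 99.5% | 83.3% |

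**Step 5. Sensitivity to the form of the test (0.025, 147 per arm; Arm C 80% / 85% / 90%).** Unpooled variance: 40.2 / 81.3 / 98.6%. Continuity-corrected: 34.5 / 76.1 / 97.5%. Exact enumeration of the z test: 39.7 / 80.8 / 98.6%. The conclusion does not depend on the variant.

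**Step 6. Size needed for 70% vs 80% at 0.025.** 356 per arm for 80% power and 464 for 90%. The latter is 464/147 = 3.2 times the planned figure.

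**The case against.** The strongest reply is that this is a one-letter slip. The opening of 9.4.2 assumes that the rifabutin regimens, with or without raltegravir, beat the double-dose arm. Section 9.6.2 then names the two tests, so an analyst following it would run C versus B at 0.025. That is probably what was meant, and no design number moves. It still leaves the only alpha-allocation sentence naming the wrong contrast, and correcting the letter does not repair the power claim.

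The protocol also puts no number on adequate, so 80% is my benchmark. That is fair, but 40% to 51% at an Arm C rate of 80% is low by any usual standard. From 85% upward the claim holds at either alpha, if only just at 0.025.

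If C versus A is secondary, 0.05 is the natural level. The shortfall then covers Arm C rates of 80% to 83.7%, about 37% of the assumed range, rather than the lower half. This stands as a refinement. The power sentence in 9.4.2 is, however, tied to a 0.025-level test, so both levels are reported.

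Finally, SAP section 1.6 says accrual period 2 will not open, so neither contrast will be tested at 147 per arm. That limits the practical effect but does not make the protocol consistent.

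**Conclusion.** Both parts hold. Section 9.4.2 contradicts 1.2, 9.5.2 and 9.6.2 on the second primary contrast; C versus B is the reading that fits the rest of the protocol and the SAP's primary hypothesis. Power is ample for C versus B (at least 99.9%). For C versus A it depends on the Arm C rate: with 147 per arm and Arm A at 70%, it falls below 80% for Arm C rates under 85.0% at two-sided 0.025, or under 83.7% at two-sided 0.05. The lowest values, at an Arm C rate of 80%, are 40% and 51%.

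These results rest on the protocol's own rates and test; only the 80% benchmark is assumed. The figures 147, 152, 157 and 471 and the 0.025 split are unaffected, because A versus B drives the sample size. This should be fixed, but it does not undermine the primary design.

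**What to change.** 1. In 9.4.2, name Arm C versus Arm B as the second primary contrast. Keep C versus A as secondary objective 1.3.3.
2. Replace the general claim of adequate power with: *With 147 per arm, C versus B has above 99% power at two-sided 0.025. C versus A (secondary, Arm A at 70%) has about 40%, 80% and 98% power at two-sided 0.025, or 51%, 87% and 99% at two-sided 0.05, for Arm C rates of 80%, 85% and 90%.*
3. In 9.6.3, state the alpha for C versus A. That section leaves secondary tests unadjusted except for unnamed suppression analyses reviewed by the DSMB, and 9.5.2 names only contrasts with Arm B for that review. Two-sided 0.05 is therefore the natural reading, but it should be written down.

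The cost is rewording in 9.4.2 and one clause in 9.6.3. Sample size, alpha split and primary test are unchanged; one stated power becomes less favourable.

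### The fixed 0.025 split for the two primary tests is valid, but a Holm step-down would raise planned power for Arm A versus Arm B from about 90% to 94% at the same nominal 5% familywise error

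*Protocol*

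**What the plan says.** Protocol section 9.4.2 states for the primary objective that "we will have two hypothesis tests and will use an alpha-level of 0.025 for each test (thus, overall alpha-level = 0.05". The test is a "two-sample, two-sided 0.025-level asymptotically-normal binomial test". The sizing rests on Arm B ("the overall virologic efficacy of the double-dose LPV/r arm is 50" percent), Arm A ("the standard LPV/r dosed arm coupled with RBT is 70% by 48 weeks") and Arm C ("and 80-90% for LPV/r and RAL with RBT-based anti-TB treatment"), and concludes that "147 participants per arm will provide 90% power to detect a 20% difference in virologic response rates by 48 weeks". Two 3% inflations, for rifampin resistance and for interim looks, take 147 to 152 and then 157 per arm, 471 in total.

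The documents do not agree on which two contrasts are meant. The sentence in 9.4.2 that sets the alpha pairs A against B with C against A. Section 9.6.2 specifies an "asymptotic normal binomial test (Arm A versus Arm B; Arm C versus Arm B". The primary objective (1.2) and the interim monitoring (9.5.2) also compare both rifabutin arms with Arm B.

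Neither document carries unused alpha from one test to the other. Section 9.6.3 leaves the secondary analyses largely unadjusted. The SAP covers the PK and safety interim analysis and the PK objectives, with no multiplicity rule for the primary endpoint.

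**The concern.** Under a fixed split, the half of alpha given to a contrast is lost to the other contrast even after the first has been won. Here that loss is avoidable. On the plan's assumptions C versus B is almost certain to be significant at 0.025, so a step-down rule would nearly always let A versus B be tested at 0.05.

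A versus B is the contrast that sets the sample size. It is also the one that speaks to rifabutin with standard-dose lopinavir/ritonavir without adding raltegravir. Power on it can be raised with no extra participants and no looser nominal familywise error.

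**Working it through.** **Inputs (section 9.4.2).** Arm B 50%, Arm A 70%, Arm C 80-90%; two-sided 0.025 per test; 147 per arm, 157 after inflation.

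**Reproducing the plan's figure.** Pooled-variance formula, no continuity correction, mean rate 0.60:

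n = [z(α/2)·√(2·0.6·0.4) + z(0.90)·√(0.5·0.5 + 0.7·0.3)]² / 0.20²

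- At two-sided 0.025: (2.2414 × 0.6928 + 1.2816 × 0.6782)² / 0.04 = 146.7, so 147. This matches the plan.
- At two-sided 0.05: (1.9600 × 0.6928 + 1.2816 × 0.6782)² / 0.04 = 124.0, so 124.
- Inflation: 147/0.97 = 151.5, so 152; 152/0.97 = 156.7, so 157; 3 × 157 = 471. This also matches.

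**Formula power for A versus B.** Power = Φ{[0.20·√n − z(α/2)·0.6928] / 0.6782}:

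- n = 147: Φ(1.286) = 90.1% at 0.025; Φ(1.573) = 94.2% at 0.05.
- n = 157: Φ(1.405) = 92.0% at 0.025; Φ(1.693) = 95.5% at 0.05.

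C versus B at n = 147 has more than 99.9% power at 0.025 even with Arm C at 80%, so Holm releases the full 0.05 to A versus B almost every time.

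**Simulated power for A versus B.** Three binomial arms, pooled z-test, at least 1,000,000 trials per row. Holm rule: the smaller p-value at 0.025 and, if rejected, the other at 0.05.

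| Pair of tests | n per arm | Arm C | Fixed split | Holm | Gain (points) |
|---|---|---|---|---|---|
| A–B and C–B | 147 | 80% or 90% | 90.4% | 94.2% | 3.7–3.8 |
| A–B and C–B | 157 | 80% or 90% | 92.0% | 95.4% | 3.4 |
| A–B and C–B | 147 | 70% | 90.4% | 93.2% | 2.8 |
| A–B and C–A | 147 | 80% | 90.4% | 93.0% | 2.6 |
| A–B and C–A | 147 | 90% | 90.3% | 94.1% | 3.8 |
| A–B and C–B | 20 | 80–90% | 16% | 21–23% | 5–7 |

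The C–A row with Arm C at 80% gains less because C versus A has only about 40% power at 0.025 and often releases nothing.

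**Error control.** If both nulls are true, Holm makes a false claim only when the smaller p-value is at or below 0.025, the same event as under the fixed split. The simulated rate is 4.2-4.7% for both rules. If only one null is true, Holm tests it at 0.05 at most. With A = B = 50% and C = 80%, A versus B is falsely rejected in about 2.3% of trials under the split and 5.4% under Holm at n = 147. At n = 157 the Holm figure is 4.8%. The excess over 5% at 147 comes from the discreteness of the normal-approximation test; Holm's nominal bound is still 5%.

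**The case against.** The strongest reply is that nothing is broken. The split is prespecified, controls the error and meets its power target. That stands: this is lost efficiency, and a reader who infers that the primary tests are invalid or the trial underpowered as designed would be wrong.

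A second reply is that the gain depends on Arm C. Section 9.4.2 itself doubts that rates of 85-90% seen in resource-rich settings can be reached here. This stands in part: with Arm C at 70% the gain is 2.8 points, and it never falls below zero.

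A third reply is that Holm is not free. When raltegravir works and rifabutin alone adds nothing, the chance of a false A-versus-B claim roughly doubles. This stands as a disclosed trade-off within the 5% familywise limit that the plan set for itself.

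A fourth reply is that the comparison will not take place at this size. SAP section 1.6 says accrual period 2 will not open, leaving about 20 per arm. This stands, and it is the main limit on practical weight.

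**Conclusion.** The point holds as a cheap improvement to a valid rule. At the planned rates, with A versus B and C versus B as the family, Holm adds about 4 points of power for A versus B at 147 per arm and about 3.4 at 157. It adds roughly 2.6 to 2.8 points under the less favourable readings examined. The figures rest on the 50%, 70% and 80-90% assumptions and on the pooled normal-approximation test. They ignore the interim looks, whose 99.995% intervals (section 9.5.2) use a negligible share of alpha.

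Three stronger readings are tempting, and the documents do not support them:

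- That the trial could safely shrink to 124 per arm. That number is the size for a plain 0.05 test, and reaching it through Holm relies on Arm C succeeding nearly always.
- That the rise from 90% to 94% is what the trial as conducted would gain. At about 20 per arm power for A versus B is about 16% with the split and 21-23% with Holm, too low to rely on either way.
- That Holm would clash with an interval already planned for the primary endpoint. Neither 9.4.2 nor 9.6.2 specifies one. The 97.5% interval in 9.5.2 is one-sided and concerns TB cure.

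**What to change.** First reconcile the contrast pair: section 9.4.2 names C against A, while 1.2, 9.5.2 and 9.6.2 compare both rifabutin arms with Arm B. A step-down rule needs one agreed family.

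Then put one sentence in 9.4.2 and 9.6.2, or in a final-analysis SAP, before efficacy data by arm are examined. For example: *The two primary contrasts will be tested by Holm's procedure at an overall two-sided 0.05. The smaller p-value is tested at 0.025 and, if it is significant, the other at 0.05.* Leave the sample size and the interim boundaries as they are.

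The cost is that sentence plus two things to acknowledge in it: a lone true null can be rejected at up to the nominal 5% instead of 2.5%, and any fixed-level confidence intervals reported beside the tests may not match every decision and should be labelled descriptive. If the 48-week comparison is reported on accrual period 1 alone, say plainly that power is low under either rule.
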